Appendix 7.	Protocol Amendment H9X-MC-GBGO(a) Summary A Randomized, Double-Blind Trial Comparing the Effect of the Addition of Dulaglutide 1.5 mg versus the Addition of Placebo to Titrated Basal Insulin on Glycemic Control in Chinese Patients with Type 2 Diabetes	90

1. Synopsis

Title of Study:

A Randomized, Double-Blind Trial Comparing the Effect of the Addition of Dulaglutide 1.5 mg versus the Addition of Placebo to Titrated Basal Insulin on Glycemic Control in Chinese Patients with Type 2 Diabetes (T2D).

Rationale:

Glucagon-like peptide-1 (GLP-1) receptor agonists and insulin are often recommended to be used concomitantly in diabetes treatment guidelines, and several studies including AWARD-9 (Study H9X-MC-GBDI) have provided efficacy and safety data of the addition of a GLP-1 receptor agonist to basal insulin (Pozzilli et al. 2017).

The purpose of study H9X-MC-GBGO (GBGO) is to evaluate the effects of the addition of once weekly (QW) dulaglutide or the addition of placebo QW to titrated insulin glargine, with metformin and/or acarbose, on glycemic control and safety in adult Chinese patients with T2D.

Objectives:

Objectives	Endpoints
Primary 
 To show the superiority of the addition of dulaglutide 1.5 mg QW compared to the addition of placebo QW to titrated basal insulin glargine, with metformin and/or acarbose, on change from baseline in hemoglobin A1c (HbA1c) after 28 weeks of treatment in patients with T2D. 	
 The change in HbA1c from baseline.
Key Secondary (controlled for Type I error) 
 To compare the addition of dulaglutide 1.5 mg QW with the addition of placebo QW to titrated basal insulin glargine for other parameters of glucose control and body weight change after 28 weeks of treatment in patients with T2D. 	
 Proportion of patients achieving HbA1c target of <7.0% Change from baseline in body weight Change from baseline in FSG (central lab)
Additional Secondary 
 To compare the addition of dulaglutide 1.5 mg QW with the addition of placebo QW to titrated basal insulin glargine for the following parameters after 28 weeks of treatment in patients with T2D. 	
 Proportion of patients achieving HbA1c target of $\leq 6.5\%$; Proportion of patients achieving HbA1c target of <7.0% and with no weight gain (<0.1 kg) at 28 weeks and without documented symptomatic hypoglycemia (BG <3.0 mmol/L) during the maintenance period (Weeks 12-28); Proportion of patients achieving HbA1c target of <7.0% at 28 weeks and without documented symptomatic hypoglycemia (BG

	
 <3.0 mmol/L) during the maintenance period (Weeks 12-28); Proportion of patients achieving HbA1c target of <7.0% and without weight gain (<0.1 kg); Changes from baseline in BG from daily self-monitored blood glucose (SMBG) profiles; Changes from baseline in daily mean insulin glargine doses

Safety:
 
 To compare the addition of dulaglutide 1.5 mg QW with the addition of placebo QW to titrated basal insulin glargine for selected safety parameters through 32 weeks in patients with T2D (unless noted otherwise). 	
 Incidence of treatment-emergent adverse events (TEAEs), serious adverse events (SAEs) and discontinuation of study drug due to adverse events (AEs); Incidence of adverse event of special interest (AESI) 
 Occurrence of hypoglycemic episodes; Incidence of initiation of rescue therapy due to severe, persistent hyperglycemia; Incidence of adjudicated and confirmed pancreatitis; Incidence of thyroid neoplasm Incidence of deaths and nonfatal cardiovascular (CV) events; Incidence of allergic and hypersensitivity AEs Change from baseline in electrocardiograms, laboratory and vital sign measurements.

Abbreviations: BG = blood glucose; CV = Cardiovascular; FSG = fasting serum glucose; HbA1c = hemoglobin A1c; SMBG = self-monitored plasma glucose; T2D = type 2 diabetes.

Summary of Study Design:

Study GBGO is a Phase 3b, multicenter, randomized, double-blind, parallel-arm trial that investigates the effect of the addition of dulaglutide 1.5 mg QW or the addition of placebo QW to titrated insulin glargine, with metformin and/or acarbose, on change in HbA1c from baseline in Chinese patients with T2D over a 28-week treatment period.

Treatment Arms and Duration:

Study GBGO will consist of 3 periods: an approximately 3-week screening/lead-in period, followed by a 28 week treatment period, and a 4-week safety follow-up period. Patients will be

randomized in a 1:1 ratio to (1) dulaglutide 1.5 mg QW as add-on to insulin glargine, or (2) placebo QW as add-on to insulin glargine, with metformin and /or acarbose. Patients will be stratified at randomization based on HbA1c (<8.5%, $\geq 8.5\%$) and oral antihyperglycemic medications (OAMs) usage (metformin alone, acarbose alone, metformin and acarbose).

Number of Planned Patients:

- Entered: 483
- Enrolled/Randomized: 290
- Completed: 246

Statistical Analysis:

Determination of Sample Size:

A total of approximately 290 patients (145 per group) will be randomized to have approximately 246 completers (123 per group) to show dulaglutide as add-on to titrated insulin glargine is superior to placebo as add-on to titrated insulin glargine with 90% power assuming a treatment difference of 0.5% in HbA1c reduction, standard deviation (SD) = 1.2%, and dropout rate of 15%. The screen failure rate (including lead in failure) is estimated as 40%. Approximately 483 patients will be screened.

Efficacy Analyses:

The primary analysis model for HbA1c will be mixed-model for repeated measures (MMRM) analysis using restricted maximum likelihood (REML) with treatment, OAM usage (metformin alone, acarbose alone, metformin and acarbose), visit, and treatment-by-visit as fixed effects, baseline as a covariate, and patient as random effect. An unstructured covariance structure will be used to model the within-patient variability and implicitly adjust for missing data.

The primary evaluation of change from baseline for body weight will be performed using MMRM on the intention to treat (ITT) population. The analyses of other secondary efficacy measures that are continuous variables will be performed using MMRM on the ITT population. For percent of patients achieving the target HbA1c of <7.0% and $\leq 6.5\%$, repeated measures logistic regression with generalized linear mixed model will be used. The model includes treatment, OAM usage (metformin alone, acarbose alone, metformin and acarbose), visit, and treatment-by-visit as fixed effects and baseline HbA1c as a covariate.

Safety Analyses:

Listings and summaries of safety data will be generated. Summary statistics will be provided for TEAEs, SAEs, and study discontinuation due to AEs or death during the treatment period. Counts and proportions of patients experiencing AEs will be reported for each treatment group, and Fisher's exact tests will be used to compare the treatment groups.

For continuous laboratory analytes, the change from baseline to endpoint will be analyzed using an analysis of variance (ANOVA) on the rank-transformed data, with treatment as a fixed effect. Last observation carried forward will be used to impute missing postbaseline values. For

subjective (qualitative) laboratory analytes, counts and proportions of patients with normal and abnormal values will be analyzed using Fisher's exact tests.

Treatment differences in incidence of hypoglycemic episodes will be assessed by a Fisher's exact test. Treatment differences in rates of hypoglycemic episodes will be assessed by the generalized linear mixed-effects (GLM) model for negative binomial distribution. The model will include treatment, OAM usage (metformin alone, acarbose alone, metformin and acarbose), visit, treatment-by-visit interaction, and baseline hypoglycemia rate.

Time to initiation of rescue therapy due to severe, persistent hyperglycemia will be analyzed using the semiparametric proportional hazard Cox model with treatment, and OAM usage (metformin alone, acarbose alone, metformin and acarbose) as fixed effects and baseline HbA1c as a fixed covariate. The proportions of patients initiating rescue therapy due to severe, persistent hyperglycemia will be analyzed using Fisher's exact tests.

2. Schedule of Activities

Table GBGO.1. Schedule of Activities

	Screening/Lead In		Treatment Period																Safety Follow-Up	
			1	2	3 ^a	4	5	6	7	8	9	10	11	12	13	14	15	16	17	
Visit			1	2	3 ^a	4	5	6	7	8	9	10	11	12	13	14	15	16	17	ET ^b
Week of Treatment	-3	-2	0	1	2	4	5	6	7	8	10	12	15	18	21	24	28			32
Allowable Deviation (\pm Days)	± 7	± 3	0	± 3	± 3	± 4	± 2	± 4	± 2	± 4	± 2	± 7	± 7	± 7						
Fasting visit ^c					X									X				X	X	
Telephone visit									X	X		X		X		X				
Informed consent	X																			
Randomization			X																	
Clinical Assessments																				
Demography ^d	X																			
Medical history	X																			
Previous diabetes therapy	X																			
Physical examination	X																	X	X	
Height	X																			
Weight	X		X			X				X		X		X		X	X	X	X	X
Vital signs (BP and PR ^e)	X	X	X	X	X	X		X		X		X		X		X	X	X	X	X
Electrocardiogram ^f	X																	X	X	
Preexisting conditions and adverse events	X	X	X	X	X	X	X ^g	X	X	X	X	X								
Concomitant medications	X	X	X	X	X	X	X ^h	X	X	X	X	X								
Review/record hypoglycemic events		-	X	X	X	X	X ⁱ	X	X	X	X									
Patient summary																		X	X	X
Patient Education																				
Dietary and exercise counseling and BG management training ^j		X	X																	
BG meter and SMBG training		X	X																	
SUP training and SoloStar pen training ^k		X	X																	
Dispense BG meter/supplies ^l		X	X	X	X	X		X		X		X		X		X		X		
Dispense study diary, instruct in use		X	X	X	X	X		X		X		X		X		X	X ^m	X		

	Screening/Lead In		Treatment Period															Safety Follow-Up	
			1	2	3 ^a	4	5	6	7	8	9	10	11	12	13	14	15	16	
Visit																			801
Week of Treatment	-3	-2	0	1	2	4	5	6	7	8	9	10	11	12	13	14	15	16	32
Allowable Deviation (±Days)	±7	±3	0	±3	±3	±4	±2	±4	±2	±4	±2	±7	±2	±7	±2	±7	±2	±7	±7
Fasting visit ^c			X									X					X	X	
Telephone visit							X		X		X		X		X				
Review and transfer to eCRF/return study diary				X	X	X	X		X		X		X		X	X	X		X
Remind patients about 7 point SMBG ^a		X								X						X			
Review/record 7-point SMBG values			X										X				X	X ^d	
Review fasting/4-point BG from SMBG ^f			X	X	X	X	X	X	X	X	X	X	X	X	X	X	X	X	
Review study drug usage			X	X	X	X		X		X		X		X		X	X	X	
Review insulin dose and adjustment per TTT algorithm ^g			X	X	X	X	X	X	X	X	X	X	X	X	X	X	X	X	
Dispense study drug and injection supplies			X			X				X				X					
Observe patient inject dulaglutide QW			X																
Patient returns study drug and injection supplies				X	X	X		X		X		X		X		X	X	X	
Assess dulaglutide compliance						X				X		X		X		X	X	X	
Assess compliance with weekly insulin dose adjustment per TTT algorithm					X	X	X		X ^e		X ^e		X ^e		X	X	X	X	
Laboratory tests																			
Serum pregnancy test ^a	X																		
Urine pregnancy test ^t			X													X	X	X	
Follicle-stimulating hormone test ^u	X																		
Chemistry panel	X															X ^v	X ^v		
Serum creatinine, eGFR (CKD-EPI) ^w	X		X													X	X		
Urinary albumin/creatinine			X													X	X		
Calcitonin	X		X													X	X		
Hematology	X															X	X		

	Screening/Lead In		Treatment Period															Safety Follow-Up	
			1	2	3 ^a	4	5	6	7	8	9	10	11	12	13	14	15	16	
Visit																			801
Week of Treatment	-3	-2	0	1	2	4	5	6	7	8	9	10	11	12	13	14	15	16	32
Allowable Deviation (±Days)	±7	±3	0	±3	±3	±4	±2	±4	±2	±4	±2	±7	±2	±7	±2	±7	±2	±7	±7
Fasting visit ^c			X										X				X	X	
Telephone visit							X		X		X		X		X				
Fasting serum glucose			X									X					X	X	
HbA1c	X		X								X					X	X		
Lipid panel			X														X	X	
Pancreatic enzymes	X		X														X	X	X
Health Outcomes																			
EQ-5D-5L			X									X					X	X	
IW-SP			X								X					X	X		
MDDAB Module 1: SUP Ease of Use								X									X	X	
MDDAB Module 2: SUP Device Features								X									X	X	
MDDAB Module 3a: SUP Experience (interim evaluation)								X											
MDDAB Module 3b: SUP Experience (end of study evaluation)																X	X		
MDDAB Module 4: Glargine Delivery Device Experience																X	X		

Abbreviations: 801 = safety follow-up visit; BG = blood glucose; BP = blood pressure; CV = cardiovascular; D = days; eCRF = electronic case report form; EQ-5D-5L = EuroQol 5-dimension questionnaire; ET = early termination; FSH = follicle-stimulating hormone; GAD = glutamic acid decarboxylase; HbA1c = hemoglobin A1c; ICA = islet cell antibodies; IWRS = interactive web response system; IW-SP = Impact of Weight on Self-Perception Scale; MDDAB = Medication Delivery Device Assessment Battery; PR = pulse rate; Rand = randomization; SMBG = Self-Monitored Plasma Glucose; SUP = Single-Use Pen; TTT = treat-to-target.

- ^a IWRS for randomization should be accessed after all baseline assessments have been completed.
- ^b Patients who are unable or unwilling to continue in the study for any reason will perform an ET visit. If the patient is discontinuing during an unscheduled visit, that visit should be performed as the ET visit. If the patient is discontinuing during a scheduled visit, that visit should be performed as an ET visit. 801 (Safety Follow-Up Visit) should be performed 4 weeks after the ET visit as the final study visit.
- ^c Before visits at which laboratory tests will be conducted, patients should be reminded to report to the site in a fasting condition, after a period of approximately 8 hours without eating, drinking (except water), or any significant physical activity, and before taking their study drug, metformin and/or

acarbose, and insulin glargine, if administered before breakfast.

- d. Demographics include patient birth year, sex.
- e. Site should record all results on the eCRF
- f. Single tracing, performed locally (see Section 9.4.1).
- g. Preexisting conditions and adverse events will be reviewed during telephone contacts but recorded on the eCRF at subsequent office visits.
- h. Concomitant medications will be reviewed during telephone contacts but recorded on the eCRF at subsequent office visits.
- i. Hypoglycemic events will be reviewed during telephone contacts but recorded on the eCRF at subsequent office visits.
- j. Patient training should occur at Visit 2. Additional training can also be performed at Visit 3, when needed. Patient training will include training on TTT insulin dose adjustment algorithm.
- k. Retraining and review of device training to be performed as needed.
- l. Dispense only as needed.
- m. Safety data to be captured after discontinuation of study drug during safety follow-up period.
- n. Patients will be asked to perform two 7-point SMBG profiles on two nonconsecutive days, in the 2-week period prior to Visit 3, as well as prior to Visit 12 and Visit 17. A 7-point SMBG consists of measurements before and 2 hours after each of 3 main meals within the same day and at bedtime. If 7-point SMBG is not performed, then data from the most recent nonconsecutive 4-point SMBG (3 before each meal and one at bedtime) profiles can be used. If more than 2 SMBG profiles are available, the 2 most recent profiles on nonconsecutive days should be used. In the weeks that the 7-point profiles are performed, the 4-point SMBG profiles will not be needed.
- o. Review/record 7-point SMBG profile(s), only if applicable, based on previous study visit.
- p. Patients will be encouraged to collect a daily fasting BG and a weekly 4-point SMBG. Missing a fasting BG measurement will not be considered a protocol deviation.
- q. Insulin dose assessment and dose adjustment should be done at least 3 days prior to Visit 3 to ensure the collection of at least 3 days of FBG for patient eligibility assessment prior to randomization. The insulin glargine dose should be reduced by 20% at Visit 3 if baseline HbA1c \leq 8.0%. Further dose adjustments are to start at Visit 6 per the TTT algorithm, and before that only in certain situations (for details see Section 5.1). The TTT algorithm should be used for dose adjustments until the last visit on randomized treatment (Visit 17 or ET Visit). After discontinuation of study drug, the investigator will decide on the most appropriate therapeutic regimen, and if applicable, the most appropriate insulin dose adjustment schedule. Refer to Protocol Section 7.2.2.2 for complete instructions on insulin dose adjustment.
- r. Assessment of the patient's compliance to the TTT algorithm will be collected in the eCRF at Visits 8, 10, and 12 for the period since the previous visit.
- s. A serum pregnancy test will be performed at Visit 1 for women of childbearing potential only.
- t. A urine pregnancy test will be performed at Visit 3, with the result available prior to randomization and first injection of study drug, and at additional visits as shown in the schedule, for women of childbearing potential only. Additional pregnancy tests will be performed at the investigator's discretion or if required per local regulations and/or institutional guidelines during the study.
- u. Follicle-stimulating hormone test will be collected at Visit 1 for postmenopausal women at least 45 years of age with an intact uterus, not on hormone therapy, and who have had spontaneous amenorrhea for more than 6 months and less than 12 months and estradiol levels consistent with a postmenopausal state (FSH \geq 40 mIU/mL and estradiol $<$ 30 pg/mL). After Visit 1, additional tests may be performed at the investigator's discretion during the study.
- v. For those visits when fasting glucose is required, glucose will not be included in the chemistry panel.
- w. Chronic Kidney Disease-Epidemiology (CKD-EPI) equation will be used to estimate the glomerular filtration rate.

3. Introduction

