[11] Women of child-bearing potential who are abstinent (if this is complete abstinence, as their preferred and usual lifestyle) or in a same sex relationship (as part of their preferred and usual lifestyle) must agree to either remain abstinent or stay in a same sex relationship without sexual relationships with males. Periodic abstinence (e.g., calendar, ovulation, symptothermal, post-ovulation methods), declaration of abstinence just for the duration of a trial, and withdrawal are not acceptable methods of contraception.

Otherwise, women of child-bearing potential participating must agree to use one highly effective (less than 1% failure rate) method of contraception or use a combination of two effective methods of contraception until plasma concentration equals or is lower than the [NOAEL for embryo fetal effects].

[a] Women of child-bearing potential participating must test negative for pregnancy prior to initiation of treatment as indicated by a negative serum pregnancy test at the screening visit followed by a negative urine pregnancy test within 24 hours prior to exposure.

[b] Either one highly effective method of contraception (such as combination oral contraceptives implanted contraceptives or intrauterine devices) or a combination of two effective methods of contraception (such as male or female condoms with spermicide, diaphragms with spermicide or cervical sponges) will be used. The subject may choose to use a double barrier method of contraception. Barrier protection methods without concomitant use of a spermicide are not a reliable or acceptable method. Thus, each barrier method must include use of a spermicide. It should be noted that the use of male and female condoms as a double barrier method is not considered acceptable due to the high failure rate when these methods are combined.

Women not of childbearing potential may participate and include those who are:

[a] infertile due to surgical sterilization (hysterectomy, bilateral oophorectomy, or tubal ligation), congenital anomaly such as mullerian agenesis; or

[b] post-menopausal – defined as either

- i. A woman at least 40 years of age with an intact uterus, not on hormone therapy, who has cessation of menses for at least 1 year without an alternative medical cause, AND a follicle-stimulating hormone >40 mIU/mL; or
- ii. A woman 55 or older not on hormone therapy, who has had at least 12 months of spontaneous amenorrhea; or

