Appendix 2. Clinical Laboratory Tests

Clinical Laboratory Tests^{a,c}**Hematology**

Hemoglobin
Hematocrit
Erythrocyte count (RBC)
Mean cell volume
Mean cell hemoglobin concentration
Leukocytes (WBC)
Neutrophils, segmented
Lymphocytes
Monocytes
Eosinophils
Basophils
Platelets

Urinalysis

Albumin/creatinine ratio (urine)^b

Endocrine

Calcitonin

Lipid Panel

Total cholesterol
LDL^g
HDL
VLDL
Triglycerides

Pregnancy test serum and urine^e**Clinical Chemistry****Serum Concentrations of:**

Sodium
Potassium
Total bilirubin
Direct bilirubin
Alkaline phosphatase
Alanine aminotransferase (ALT)
Aspartate aminotransferase (AST)
Gamma-glutamyl transferase (GGT)
Blood urea nitrogen (BUN)
Creatinine
Creatine kinase (creatinine phosphokinase; CPK)^d
Uric acid
Calcium
Glucose
Albumin

eGFR (calculated by CKD-EPI equation)

Fasting glucose**Pancreas (Exocrine)**

Serum amylase, total and pancreatic
Serum lipase

HbA1c**Follicle-stimulating hormone^f**

Abbreviations: CKD-EPI = Chronic Kidney Disease-Epidemiology; CK-MB = creatine kinase-MB; eGFR = estimated glomerular filtration rate; HbA1c = hemoglobin A1c; HDL = high-density lipoprotein cholesterol; LDL = low-density lipoprotein cholesterol; RBC = red blood cells; WBC = white blood cells; VLDL = very low density lipoprotein cholesterol.

- ^a All tests will be performed by a Lilly-designated central laboratory, unless otherwise noted.
- ^b Urinary albumin and creatinine are measured; the ratio is calculated.
- ^c Additional blood samples may be collected based on the investigator's judgment.
- ^d CK-MB is to be assayed if the creatine kinase result is >1000 IU/L.
- ^e Serum pregnancy test will be performed by central laboratory at Visit 1 for women of childbearing potential; a urine pregnancy test must be performed at Visit 3. Urine pregnancy tests may also be performed at the investigator's discretion during the study. A local laboratory may be used for urine pregnancy tests.
- ^f Follicle-stimulating hormone test performed at Visit 1 for potential postmenopausal women age 45 years or above with an intact uterus, not on hormone therapy or oral contraceptives, and who have had spontaneous amenorrhea for more than 6 months and less than 12 months and estradiol levels consistent with a postmenopausal state (FSH \geq 40 mIU/mL and estradiol <30 pg/mL).

^g This value will be calculated. If triglycerides >400 mg/dL, then direct LDL will be assayed.

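### The scheduled Visit 1 FSH test covers women with under 12 months of amenorrhoea, but the only category that uses FSH requires at least 1 year, so the scheduled result informs no part of inclusion criterion 11

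*Protocol*

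**What the plan says.** Three places in the protocol bear on this.

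- **Section 2, Schedule of Activities, footnote u:** "Follicle-stimulating hormone test will be collected at Visit 1 for postmenopausal women at least 45 years of age with an intact uterus". The women must not be on hormone therapy and must have "spontaneous amenorrhea for more than 6 months and less than 12 months and estradiol levels consistent with a postmenopausal state". The footnote then gives limits of FSH at or above 40 mIU/mL and estradiol below 30 pg/mL, and allows further tests after Visit 1 at the investigator's discretion.
- **Appendix 2, footnote f:** "Follicle-stimulating hormone test performed at Visit 1 for potential postmenopausal women age 45 years or above with an intact uterus", again with "spontaneous amenorrhea for more than 6 months and less than 12 months" and the same FSH and estradiol limits. It also excludes women on oral contraceptives, which footnote u does not.
- **Section 6.1, criterion [11], women not of child-bearing potential, postmenopausal category [b] i:** "A woman at least 40 years of age with an intact uterus, not on hormone therapy", with "cessation of menses for at least 1 year without an alternative medical cause, AND a follicle-stimulating hormone >40 mIU/mL".

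The other two postmenopausal categories, [b] ii and [b] iii, start at age 55 and do not use FSH. Nor does category [a], infertility from surgery or congenital anomaly.

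**The concern.** A screening test should be drawn in the women whose classification depends on it. Here the criterion asks for FSH in one group and the schedule draws it in another.

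Child-bearing status matters for participant protection. Footnotes s and t of the Schedule restrict the serum pregnancy test at Visit 1, and the urine tests from Visit 3 on, to women of child-bearing potential. Criterion 11 ties the contraception or abstinence requirement to the same status. If sites cannot tell from the protocol who counts as postmenopausal, they may apply these safeguards inconsistently.

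**Working it through.** No sample size, power or error-rate figure enters this point. The check sets the conditions side by side, with m for months without menses at Visit 1.

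| | Scheduled FSH test (footnotes u and f) | Criterion 11, category [b] i |
|---|---|---|
| Age | at least 45 | at least 40 |
| Uterus | intact | intact |
| Hormone therapy | none (footnote f: nor oral contraceptives) | none |
| Amenorrhoea | 6 < m < 12 | m ≥ 12 |
| FSH limit | ≥ 40 mIU/mL | > 40 mIU/mL |
| Estradiol | < 30 pg/mL | not used |

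**Step 1, overlap.** The test needs m < 12 and the category needs m ≥ 12. No value of m meets both, so at Visit 1 no woman of any age is both scheduled for the test and able to meet [b] i.

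**Step 2, use of the scheduled result.** A tested woman fails [b] i on duration. Categories [a], [b] ii and [b] iii do not use FSH. Her result therefore cannot change her status under any category of criterion 11.

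**Step 3, who needs FSH and is not scheduled for it.** From age 55, a woman not on hormone therapy with at least 12 months of amenorrhoea qualifies under [b] ii without FSH. Category [b] i therefore matters in practice for ages 40 to 54. Women aged 40 to 44 fall outside the scheduled test on both age and duration; women aged 45 to 54 fall outside it on duration.

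**Step 4, smaller mismatches.**
- An FSH of exactly 40 mIU/mL meets the footnotes' limit but not the criterion's.
- Both footnotes refer to an estradiol level, but estradiol has no row in the Schedule and is not in the Appendix 2 test list.
- Both footnotes describe the women to be tested partly by an FSH level that the test itself would supply.

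**Step 5, consequence of a missing value.** Category [b] i joins its conditions with AND. A woman without an FSH value does not meet it, and unless another category applies she stays of child-bearing potential. She then has the pregnancy tests and the contraception or abstinence requirement.

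**Step 6, the remaining gap.** Footnote u calls women with under 12 months of amenorrhoea postmenopausal, and criterion 11 does not. A site working from the Schedule could take that label as the classification and omit the safeguards in Step 5.

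**The case against.** The case on the other side accepts the conflict in wording and disputes its consequences. Much of it stands.

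- **A reader might infer that women aged 40 to 54 are bound to be enrolled in breach of the criterion, with a risk of fetal exposure.** The text does not support that. Criterion 11 admits women of child-bearing potential as well as those not of child-bearing potential, so failing [b] i is not in itself ineligibility. A missing value leads to more protection. Exposure would require a site to depart from the criterion.
- **A reader might infer that FSH can never inform the criterion.** That is true only of the scheduled Visit 1 test. Footnote u allows discretionary tests after Visit 1, and eligibility is still being reviewed at Visits 2 and 3 (Section 5.1). Appendix 2 footnote c allows extra blood samples on the investigator's judgment. Category [b] i does not require a Visit 1 or central-laboratory value, so an earlier result could serve. A woman just short of 12 months at Visit 1 could also pass 12 months by Visit 3, about 3 weeks later, although the protocol does not say that status is reassessed.
- **The footnotes may only trigger a test, with criterion 11 governing status.** This is a fair reading of footnote f, which speaks of potential postmenopausal women. It fits footnote u less well, because that footnote omits the qualifier.
- **Estradiol is secondary.** Category [b] i does not use it, so its absence from the test list does not affect that criterion.

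These points limit the harm but leave the mismatch. Discretion to draw a sample does not correct a schedule that directs the test to women for whom the result has no use under criterion 11, and nothing tells sites to draw FSH in the women who need it.

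**Conclusion.** The concern holds as an internal contradiction. The scheduled test and the category that needs it do not overlap at Visit 1, the scheduled result feeds no category of criterion 11, and women aged 40 to 54 who rely on [b] i have no scheduled FSH test.

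The size is modest. The criterion's own default is protective, and the residual risk runs only through sites that follow footnote u's label. The documents give no breakdown of the planned 290 randomised patients by sex, age or menopausal status, so the number of women affected cannot be stated. Those with a usable earlier or discretionary FSH result would not be affected.

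The conclusion assumes that amenorrhoea is judged at Visit 1, when the test is drawn, and that criterion 11 rather than a Schedule footnote decides child-bearing status. The primary analysis, power and type I error do not depend on this point. It should be corrected because it concerns participant protection and is cheap to resolve, not because it threatens the trial's conclusions.

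**What to change.** Reconcile Schedule of Activities footnote u, Appendix 2 footnote f and criterion [11] postmenopausal category [b] i on four items: age, duration of amenorrhoea, FSH limit (at or above 40, or above 40) and whether estradiol plays a part. The result should meet two conditions:

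- FSH is drawn in the women whose classification depends on it.
- The footnotes do not label as postmenopausal any woman whom criterion 11 does not.

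If estradiol is kept, it needs a place in the Schedule and in the Appendix 2 list. The difference between the footnotes on oral contraceptives should be settled at the same time. Which definition applies is a clinical decision for the sponsor.

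The cost is a protocol clarification and possibly a few more or fewer FSH samples; the test is already listed in Appendix 2. Adding estradiol would mean one further assay in the women concerned.
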